Title: Comparing right colon adenoma and hyperplastic polyp miss rate in colonoscopy using water exchange and carbon dioxide insufflation: A prospective randomized controlled trial

INTRODUCTION

Colonoscopy is currently regarded as the gold standard to detect and prevent colorectal cancer (CRC) [1]. It is estimated to prevent about 76%-90% of CRC [2], but post-colonoscopy CRCs (PCCRCs) still occur. Recent case-control studies consistently demonstrated that protection by colonoscopy against right-sided colon cancer, ranging from 40% to 60%, was lower than the 80% protection attained in the left colon [3-5]. Of all PCCRCs, 58% were attributed to lesions missed during examination [6]. In a systematic review of tandem colonoscopy studies, a 22% pooled miss-rate for all polyps was reported [7]. Colonoscopy maneuvers helping to reduce miss-rate for all polyps, particularly in the right colon, have the potential to decrease the incidence of PCCRCs.

Water exchange (WE) colonoscopy is characterized by the gasless insertion to the cecum in clear water and maximizing cleanliness during insertion. WE colonoscopy has been shown to improve the overall adenoma detection rate (ADR), compared to air insufflation colonoscopy, in many prospective randomized controlled trials (RCTs) [8-13]. WE colonoscopy also has been shown to improve right colon ADR in RCTs [10-12] and meta-analyses [14,15]. In a pooled data from two multisite RCTs, WE also significantly increases right colon combined advanced and sessile serrated ADR as compared to air insufflation colonoscopy [16]. Decreased multitasking-related distraction from cleaning maneuvers has been the most recently identified explanation for the increase in ADR by WE [17]. The right colon is usually the worst prepared segment and proximal colorectal neoplasms with advanced histology

frequently are smaller than the ones in the left colon or have a nonpolypoid appearance [18,19]. Therefore, the adoption of WE in the right colon might be especially beneficial.

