Upon arriving at the cecum, CO2 insufflation will be used in both groups and the scope will be withdrawn from the cecum to the hepatic flexure, with inspection of the mucosa at the same time. All polyps identified will be resected and sent for pathology evaluation. The most distal part of the hepatic flexure will be marked by a forceps biopsy and then the scope will be reinserted into the cecum by the first endoscopist using CO2 insufflation. A tandem inspection of the right colon will then be performed by a second endoscopist blinded to the insertion method in both study groups. All polyps found herein will be counted as the missed polyps. After the second withdrawal to the mark of distal hepatic flexure, the remainder of the colon will be examined in a standard manner by the first endoscopist. To assess the adequacy of blinding, the second endoscopist will be asked at the end of tandem right colon examination to guess which insertion method has been used. If less than 66% of these answers are correct, then adequate blinding will be considered to have

been achieved.

Polyp search and resection will be performed during the withdrawal phase in both groups. Insertion polypectomy will not be performed. All proximal colon polyps will be removed irrespective of their size and appearance. All diminutive polyps with hyperplastic appearance (based on narrow band imaging) in the rectosigmoid colon will be documented by photography and left alone. Polyp size will be determined by comparison with an opened biopsy forceps or a snare.

In both groups, the following information will be recorded: bowel preparation quality using the Boston Bowel Preparation Scale (BBPS) score [29]; the total amount of sedative medications (in procedures with sedation); the length of colonoscopy reaching cecum; the amount of water infused and suctioned during insertion and withdrawal phases; the procedure time taken for insertion and withdrawal for the first examiner; the procedure time taken for tandem right colon inspection; the need of abdominal compression and/or positon change to assist colonoscopy insertion; the overall polyp number, size, histology and location; the missed right colon polyp number, size, histology and location.

Definition

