Summary statistics will be presented as frequencies and percentages in the case of categorical variables and as the means with standard deviations (SD) in the case of continuous variables. Analysis will be performed by using an Intention-to-treat (ITT) approach. Interim analysis will be performed after enrollment of 131 patients. Student's *t*-test for continuous factors, Wilcoxon rank sum test for ordinal variables (such as polyp size), and Chi-square test for categorical variables will be used to assess differences in demographic and clinical characteristics of patients in each group. Factors associated with adenoma detection by the first examiner will be identified by univariate analysis. Factors with a *P* value <0.1 on univariate analysis will be further entered into forward stepwise logistic regression analysis. The adjusted odds ratio with 95% confidence interval (CI) will be used to describe the

influence of various factors on adenoma detection. All statistical analyses will be performed by using SAS version 9.3 or later (SAS Institute Inc., Cary, NC, USA). The criterion for statistical significance will be P value <0.05 .

REFERENCES:

6. le Clercq CM, Bouwens MW, Ronagh EJ, et al. Postcolonoscopy colorectal cancers are preventable: a population-based study. *Gut* 2014;63:957-963.
7. van Rijn JC, Reitsma JB, Stoker J, Bossuyt PM, van Deventer SJ, Dekker E. Polyp miss rate determined by tandem colonoscopy: a systemic review. *Am J Gastroenterol* 2006;101:343-350.

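### The stepwise model for adenoma detection does not force in study arm or the stratifiers and does not exclude post-randomisation variables, so it cannot supply a dependable water exchange effect on detection

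*Combined protocol and SAP*

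**What the plan says.** The combined protocol and SAP sets the rule under Statistical analysis: "Factors associated with adenoma detection by the first examiner will be identified by univariate analysis". Those with P<0.1 "will be further entered into forward stepwise logistic regression analysis". The adjusted odds ratio and its 95% confidence interval are then to describe the "influence of various factors on adenoma detection". The section gives no candidate list, no limit to baseline variables, no term that must stay in the model, and no entry level for the stepwise step.

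Randomization stratifies by colonoscopist and indication. Colonoscopy Procedures itemises the data to be recorded, among them "bowel preparation quality using the Boston Bowel Preparation Scale (BBPS) score", "the amount of water infused and suctioned during insertion and withdrawal phases" and "the procedure time taken for insertion and withdrawal for the first examiner". Definition adds separate stopwatch times for cleaning, inspection and polyp treatment, and defines withdrawal time as a total that includes biopsy and polypectomy. Study Outcomes names overall ADR as a secondary outcome.

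**The concern.** A selection rule of this kind keeps study arm only if arm earns its place. In a randomised trial, the arm contrast should be in any model from which a treatment effect might be read, and so should the factors used to stratify the allocation.

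The rule also admits any process measure associated with detection. Some of these may lie on the route by which WE acts. The Introduction says: "Decreased multitasking-related distraction from cleaning maneuvers has been the most recently identified explanation for the increase in ADR by WE". Conditioning on such a variable takes out part of the effect, and what remains for arm is not the total effect. Total withdrawal time raises a different problem. Finding and removing an adenoma lengthens it, so the outcome partly causes the predictor.

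At stake is the adjusted comparison of ADR between arms. Statistical analysis assigns its t, Wilcoxon and Chi-square tests to demographic and clinical characteristics and assigns none explicitly to ADR. A reader of the results could therefore take the stepwise odds ratio as the WE effect on detection, or take its absence as evidence of no effect.

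**Working it through.** **Plan's own figure.** The plan gives none for this model. The check uses the enrolment figure from Sample size estimation: 131/0.90 = 145.6, rounded up to 146 per arm, and 2 × 146 = 292, as stated.

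**Step 1: when each variable is fixed.**

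| Variable | Section | Fixed before randomisation? | Link to arm or outcome |
|---|---|---|---|
| Colonoscopist, indication | Randomization | Yes | Stratifiers |
| Age; demographic and clinical characteristics | Participants; Statistical analysis | Yes | None by design |
| Boston Bowel Preparation Scale (BBPS) | Colonoscopy Procedures | No | May be changed by WE, which cleans during insertion |
| Water volumes | Colonoscopy Procedures | No | Largely set by arm |
| Cleaning time | Definition | No | The CO2 arm does all its cleaning on withdrawal |
| Total withdrawal time | Definition | No | Contains biopsy and polypectomy time |
| Inspection time | Definition | No | Timed apart from polyp treatment |

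The circularity of total withdrawal time follows from its definition and needs no simulation.

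**Step 2: chance that arm fails the P<0.1 screen.** The documents give no ADR, so the rates p0 (CO2) and p1 (WE) are assumptions. With n = 146 per arm and p̄ the mean of the two rates:

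power = Φ{[(p1 − p0) − 1.645·√(2p̄(1−p̄)/n)] / √([p0(1−p0) + p1(1−p1)]/n)}

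- 40% v 50%: (0.100 − 1.645 × 0.0582)/0.0579 = 0.07; power 0.53; fails about 47%.
- 40% v 55%: (0.150 − 1.645 × 0.0584)/0.0578 = 0.93; power 0.82; fails about 18%.
- 45% v 50%: (0.050 − 1.645 × 0.0584)/0.0584 = −0.79; power 0.21; fails about 79%.

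**Step 3: effect of adjusting for a mediator.** For 40% v 55% the odds ratio is (0.55/0.45)/(0.40/0.60) = 1.83. If a variable carries a share s of the log odds ratio, the direct effect is 1.83^(1−s): 1.83, 1.35 and 1.00 for s = 0, 0.5 and 1.

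**Step 4: simulation of the rule.** There were 600 replicates with 146 per arm, the P<0.1 screen, then forward entry at P<0.05 (assumed). Candidates were arm, age, sex and one mediator. Further assumptions: WE shifts the mediator by 0.8 SD; log odds 0.4 per SD of age and 0.5 for sex. The odds ratios come from models with all the named terms in; the retention rates come from the stepwise rule.

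| ADR | Share mediated | WE OR, mediator in | WE OR, baseline factors only | Arm retained, mediator a candidate | Arm retained, baseline candidates only |
|---|---|---|---|---|---|
| 40% v 55% | 0% | 1.87 | 1.86 | 70% | 72% |
| | 50% | 1.36 | 1.80 | 22% | 68% |
| | 100% | 1.00 | 1.74 | 2% | 64% |
| 40% v 50% | 0% | 1.50 | 1.49 | 36% | 37% |
| | 50% | 1.22 | 1.50 | 19% | 37% |
| | 100% | 1.00 | 1.48 | 3% | 35% |

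Simulation error on the percentages is about 2 points. The stated rates apply at average age and sex and at the CO2 arm's mean mediator value. The crude contrast is therefore slightly smaller, and arm failed the simulated screen more often than in Step 2 (53% to 55% for 40% v 50%; 21% to 26% for 40% v 55%).

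**Step 5: a second set of assumptions.** BBPS was taken as the mediator, with total WE odds ratios of 1.78, 1.87 and 1.85. Adding BBPS gave 1.01, 1.29 and 1.49. Arm was dropped in 98.5%, 83.7% and 66.0% of trials, against 34.7%, 28.7% and 30.2% with baseline candidates only. The direction is the same.

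**The case against.** The strongest reply is that this model was never meant to estimate the WE effect. Its stated aim is to describe factors associated with detection, process measures are legitimate candidates for that aim, and the primary outcome, the right colon combined miss rate, does not use it. All of that stands. A reader might infer that the plan's adjusted WE odds ratio does condition on mediators, or that the candidates are nearly all post-randomisation. The documents support neither. The list in Colonoscopy Procedures says what is recorded, not what is offered to the model, and baseline candidates exist (both stratifiers, age, other patient characteristics).

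The mediation figures are also assumed. The explanation in the Introduction is distraction from cleaning, which is not the same thing as a BBPS score. With no mediation, offering the extra variable does essentially no harm: arm is retained in 70% of replicates against 72%. The loss of about 30% in that row therefore reflects limited power and the selection rule, not mediators. The 100% rows give an odds ratio of 1.00 by construction. For withdrawal time, the plan already times inspection separately and nowhere says that the total will be a candidate.

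The reply does not remove the gap. The rule as written permits each of these outcomes, and no other adjusted estimate of ADR by arm is specified to set beside it. A Chi-square test of ADR by arm may well be intended, but the section does not say so.

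**Conclusion.** The point holds as a gap in the specification of a secondary analysis. Following the stated rule can drop study arm, can yield a WE odds ratio that is not the total effect and may be attenuated, and can admit a predictor partly caused by the outcome. The first possibility needs only the rule itself. The other two depend on which variables are offered and selected.

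The size cannot be fixed from the documents, which give neither an ADR nor a mediation strength. Under an assumed 40% v 55%, the adjusted odds ratio lies anywhere from about 1.87 to 1.00, and arm is lost in about 30% of trials before any mediation. A smaller true difference makes the loss more frequent. It would go too far to infer that the trial's main conclusion is at risk, or that attenuation is certain.

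**What to change.** Under Statistical analysis, prespecify a logistic model for ADR by study arm, with arm, colonoscopist and indication forced in together with named baseline factors such as age and sex. Admit no post-randomisation variables. Report the arm odds ratio with its 95% confidence interval from this model, whatever its P value.

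The model is affordable. It has six parameters besides the intercept: one for arm, one for two colonoscopists, two for three indications, and one each for age and sex. At an assumed average ADR of 47.5%, 292 patients give 0.475 × 292 ≈ 139 events, or about 23 per parameter.

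Keep the stepwise factor model if wanted, but label it exploratory, list its candidates, and use inspection stopwatch time in place of total withdrawal time. State that any arm odds ratio from it is not the total WE effect.

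The cost is SAP wording and one extra model on data already being collected. The downside is that the stepwise results carry less weight in the report.
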